9 STATISTICAL CONSIDERATIONS

9.1 Study Design/Endpoints

9.1.1 Design

This is a pilot study to assess the hematologic activity and safety of Metformin in the Fanconi Anemia patient population.

9.1.2 Endpoints

Primary endpoint:

The primary endpoint is the proportion of subjects with a hematologic response.

Secondary endpoints:

- Secondary hematologic endpoints will evaluate change from baseline in:
 - hemoglobin
 - red cell transfusion requirements
 - platelet count
 - absolute neutrophil count
 - marrow cellularity
 - methylcellulose colony forming assays
- Safety: the proportion of subjects with adverse events by grade.
- Tolerability: median number of dose interruptions, median number of discontinuations, and proportion of patients who are able to achieve maximum dose of Metformin.
- Pharmacokinetics: pharmacokinetic profile and exposure of Metformin

Exploratory endpoints:

Exploratory biomarkers will describe change from baseline in:

- aldehyde-mediated damage
- chromosomal breakage and radial formation in response to DEB/MMC exposure
- cell cycling in CD34+ hematopoietic stem/progenitor cells
- serum insulin, fasting glucose, and oral glucose tolerance
- micronuclei formation in buccal swab samples

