1.3 Secondary Objectives

- 1.3.1 To evaluate the hemoglobin, RBC transfusion requirements, platelet count, and absolute neutrophil count.
- 1.3.2 To evaluate the hematopoiesis through evaluation of marrow cellularity and hematopoietic progenitor colony assays.
- 1.3.3 To evaluate the safety in Fanconi Anemia patients.
- 1.3.4 To describe the pharmacokinetics in Fanconi Anemia patients.
- 1.3.5 To describe the tolerability in this population at the target dose for 6 months duration.

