5.1.2 Overview of Treatment Regimen

Patients may begin therapy on any day of the week. Each dose of Metformin will be recorded in a medication diary by patients \geq age 18, and by parents of patients $<$ age 18. The medication diary will be returned to clinic staff at the end of each month. Dose modifications are described in Section 7.2. Reported adverse events and potential risks are described in Section 7. No investigational or commercial agents or therapies other than Metformin may be administered with the intent to treat the participant's cytopenias. Participants may continue to receive Metformin for up to 6 months unless they satisfy the criteria for removal from protocol therapy (see Section 5.5).

To minimize the risk of gastrointestinal upset, patients will increase the dose of Metformin over 4 weeks as follows.

For patients \geq 10 years of age:

Initiation Phase:

Metformin will be initiated at a dose of 500mg/day, increased by 500mg/day once a week up to 2000mg/day.

Timepoint	Dose
Week 1	500mg qPM
Week 2	500mg BID
Week 3	500mg qAM, 1000mg qPM
Week 4 through end of treatment	1000mg BID

Maintenance phase: Patients will continue on the maximum dose of 1000mg BID or otherwise maximum tolerated dose for 6 months total duration.

For patients \geq 6 years of age and $<$ 10 years of age:

Initiation phase:

Metformin will be administered at a dose of 500mg/day and increased by 500mg/day once a week up to 1000mg/day.

Timepoint	Dose
Week 1	500mg qPM
Week 2 through end of treatment	500mg BID

Maintenance phase: Patients will continue on the maximum dose of 500mg BID or otherwise maximum tolerated dose for 6 months total duration.

Dose Modification:

For patients who have difficulty tolerating Metformin at any point during the initiation or maintenance phases due to gastrointestinal upset or other AEs specified in section 7, the dose will be decreased by 500mg/day until a tolerated dose is achieved.

Dose interruption:

Patients must hold Metformin if they are NPO for any reason, have a period of prolonged fast more than 8 hours, a critical illness requiring IV fluids, and/or a gastrointestinal illness. The medication will be held until patient resumes regular PO intake.

Patients must hold Metformin for 24 hours prior to imaging scans which require contrast, such as CT scans. Patients may resume Metformin 24 hours after the completion of the contrast administration.

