9.7 Analysis of Safety and Tolerability

Any patient that received at least one dose of drug would be eligible for the safety set. The proportion of patients with each toxicity overall and by grade will be reported along with 90%

confidence interval. This will be reported for the toxicities that are at least possibly related and regardless of attribution. The proportion of patients who required at least one dose reduction, who required at least one dose delay, who completed therapy and achieved the goal dose (diabetes/obesity-related dosing) of Metformin will be reported along with the 90% exact binomial confidence interval. The median number of dose reductions and dose delays will also be reported.

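### The median number of discontinuations tells the reader almost nothing, and no planned tolerability measure shows who stayed at the target dose

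*Combined protocol and SAP*

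**What the plan says.** Objective 1.3.5 reads "To describe the tolerability in this population at the target dose for 6 months duration". Section 9.1.2 turns this into "median number of dose interruptions, median number of discontinuations, and proportion of patients who are able to achieve maximum dose".

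Section 9.7, in everyone who took at least one dose, plans a different list. It begins "The proportion of patients who required at least one dose reduction, who required at least one dose delay" and continues with those "who completed therapy and achieved the goal dose (diabetes/obesity-related dosing) of Metformin will be reported along with the 90% exact binomial confidence interval". It adds medians for reductions and delays, but none for discontinuations. Where 9.1.2 speaks of interruptions and maximum dose, 9.7 speaks of delays and goal dose.

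Three other sections matter:
- Section 5.1.2 sets an age-specific maximum dose, reached at the start of week 4 (age 10 and over) or week 2 (age 6 to under 10). It lets patients continue on a lower tolerated dose instead. Under its dose-interruption heading it also orders holds: "Patients must hold Metformin if they are NPO for any reason", and likewise for long fasts, critical illness needing IV fluids, gastrointestinal illness and contrast imaging.
- Section 5.5 makes removal from protocol therapy a single, final event, with its reason and date recorded in the CRF.
- Sections 5.1.2 and 5.2 have every dose entered in a diary.

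**The concern.** The summary section (2.5) says metformin would be a chronic medicine if it works, and that the pilot may lead to a larger controlled trial. A reader planning that trial needs to know how many patients stop, why they stop, and how many are still on the intended dose at the end.

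The measures in 9.1.2 serve that reader poorly. One is a median of a yes/no event. One is met on the day the maximum dose is first taken, whatever follows. One counts interruptions without saying whether holds ordered by the protocol for unrelated reasons are included. Section 9.7 is better, but it uses different terms and still has no measure of remaining at the target dose.

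**Working it through.** The documents give no numerical target or precision for tolerability, so there is no planned figure to reproduce. The inputs are the 24 planned patients (9.2), terminal discontinuation (5.5), the titration schedule (5.1.2), and end of treatment at Day 169 (5.3.11).

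**1. Median number of discontinuations.** With n = 24 the median is the mean of the 12th and 13th ordered values. If k patients stop, there are 24 − k zeros. The median is 0 when 24 − k ≥ 13, that is k ≤ 11. It is 0.5 at k = 12 and 1 at k ≥ 13.

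The exact (Clopper-Pearson) 90% interval for k/24 runs from the 5% quantile of Beta(k, 25 − k) to the 95% quantile of Beta(k + 1, 24 − k), with lower limit 0 when k = 0:

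| Patients stopping | Median | Proportion (exact 90% CI) |
|---|---|---|
| 0 | 0 | 0% (0 to 11.7%) |
| 2 | 0 | 8.3% (1.5 to 24.0%) |
| 6 | 0 | 25.0% (11.5 to 43.5%) |
| 11 | 0 | 45.8% (28.2 to 64.2%) |

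The chance that the median is 0 equals P(X ≤ 11) for X ~ Binomial(24, p). The documents give no p, so these rates are assumed: above 0.9999 at 10%, 0.999 at 20%, 0.969 at 30% and 0.787 at 40%.

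**2. Reaching the maximum dose.** It is first taken about Day 22 (age 10 and over) or Day 8 (under 10). A patient reduced or stopped directly afterwards meets the 9.1.2 endpoint with 169 − 22 = 147 or 169 − 8 = 161 days still to run.

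**3. What 9.7 adds.** Four courses, set against the measures:

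| Course | 9.1.2 maximum dose reached | 9.7 completion and goal dose, as one item | 9.7 dose reduction | On target at end |
|---|---|---|---|---|
| Reached target, stayed, completed | yes | yes | no | yes |
| Reached target, reduced, completed lower | yes | yes | yes | no |
| Reached target, soon stopped | yes | no | no | no |
| Never reached target, completed lower | no | no | yes or no | no |

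Read as two items, the goal-dose part of 9.7 behaves like the 9.1.2 column. No planned column matches the last one.

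Nor can the last column be recovered from the others. Suppose, for illustration, that 18 of 24 complete with the goal dose reached and 6 of 24 have a reduction. If all 6 reductions fall among the other 24 − 18 = 6 patients, 18 ended on target (75%, 90% CI 56.5% to 88.5%). If all 6 fall among the 18 and none returned to target, 18 − 6 = 12 did (50%, 31.9% to 68.1%). The planned proportions are identical in both cases.

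**4. Interruptions.** Neither 9.1.2 nor 9.7 defines an interruption or delay, or excludes the ordered holds of 5.1.2. Including them can only raise the count, so tolerability would look worse than it is.

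**The case against.** The strongest reply is that 9.7, read in full, already prevents a misleading report. A reader might infer from 9.1.2 that the trial could show near-perfect tolerability while almost half the patients stop. The documents do not support that. If 11 of 24 stop, completion is at most 13/24 (54%, 90% CI about 36% to 72%), and this shows whether completion and goal dose are one item or two. Reductions are reported as a proportion as well. It is equally tempting to say the endpoints cannot answer objective 1.3.5. That too goes too far, because 9.7 answers much of it. Both replies stand.

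It can also be said that the median of discontinuations appears only in the endpoint list, and that the pediatric studies cited in 2.2.2 report few stops (5 among 61 randomized in one, none for side effects in another). Both are true, but low rates make the median less useful: at 10% it is 0 almost with certainty. Being dropped without comment from 9.7 is itself a mismatch to resolve.

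Reasons for stopping are already collected, so no data are missing. That stands, and it makes the fix cheap; but 9.7 does not commit to reporting them. Section 9.7 also splits toxicities by attribution, but that does not classify interruptions.

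Finally, a reader might infer that titration makes six months at target impossible and so invalidates 1.3.5. Section 5.1.2 places titration inside a six-month total, and no analysis depends on the difference. That is a matter of wording only.

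**Conclusion.** The concern holds in limited form. One listed endpoint, the median number of discontinuations, cannot distinguish 0 from 11 stops among 24. This follows from discontinuation being a once-only event and needs no assumed rate. No planned statistic shows who remained on the target dose, because the closest one in 9.7 is ambiguous and, even on its stricter reading, counts patients who finished on a reduced dose. Interruption counts are undefined and may include ordered holds, which biases against the drug rather than for it.

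The size is minor to modest. Tolerability here is a descriptive secondary endpoint in a pilot, with no threshold or decision attached, and the primary analysis is untouched. The figures assume all 24 patients take at least one dose; a slightly smaller safety set would not change the conclusion.

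**What to change.** In 9.1.2 and 9.7:
- Replace the median number of discontinuations with the proportion discontinuing, overall and by CRF-recorded reason, with an exact 90% CI, in the safety set.
- Add the proportion still on the age-specific target dose of 5.1.2 at end of treatment, from the drug diaries, with an exact 90% CI. Count patients off therapy as not on target, and say how an ordered hold in progress at that visit is handled.
- State whether completing therapy and reaching the goal dose are one item or two.
- Define an interruption, and report those for adverse events separately from protocol-required holds.
- Use one term for interruption or delay, and one for maximum, goal or target dose.

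No dose, hold or stopping rule changes. Doses and reasons for removal are already recorded. The documents do not say that the diary captures why a dose was missed, so that reason would need coding at the diary reviews, which already take place alongside the adverse event assessments. The cost is that coding plus a short text amendment.

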9.2 Sample Size, Accrual Rate and Study Duration

The total sample size is anticipated to be 24 patients. It is anticipated that without additional treatment, only 5% of patients would achieve a hematologic response. We would be interested in Metformin as a treatment in this patient population if the hematologic response rate is 20% or higher. The trial will be single arm, one-stage trial. The treatment will be considered promising if at least 3/22 subjects have a hematologic response. The probability of observing at least 3/22 responders is at least 0.84 assuming the true response is $\geq 20\%$ and is $< 10\%$ if the true response is $< 5\%$. It is anticipated that we will need 24 patients to accrue 22 evaluable patients. Evaluable patients are defined in section 4.2.

It is anticipated that an average of 1-2 patients will enroll each month on study and the study duration is anticipated to be approximately 2 years.

9.3 Interim Analysis

Given that this is a pilot study of 24 patients, no interim analysis is planned.

The study accrual may be suspended if there are $\geq 3/24$ patients with non-hematologic non-GI grade IV events that are attributed to be at least possibly related to Metformin which are observed during any point in the study. The probability of observing 3 or more events among 24 subjects is equal to 0.89 if the observed rate is 20% and 0.12 if the observed rate is 5%.”

9.4 Patient demographic and baseline characteristics

Patient demographic and baseline characteristics, including age, gender, medical history, FA subtype, prior therapy, and baseline hematologic values (hemoglobin, platelet count, absolute neutrophil count, transfusion requirements) will be summarized using descriptive statistics. For continuous variables, descriptive statistics (number (n), mean, standard deviation, standard error, median, range) will be provided. For categorical variables, patient counts and percentages will be provided.

9.5 Analysis of Primary Endpoints

Hematologic response will be defined by the modified MDS IWG criteria²⁴ which are provided in section 6.

Among evaluable patients (as defined in Section 4.2), hematologic response rate will be estimated and will be reported along with 90% binomial confidence intervals. Estimated response rates for each individual hematologic lineage will also be reported for hemoglobin/transfusion requirements for RBCs, platelet count, and absolute neutrophil count will also be reported along with 90% binomial confidence intervals. The time to hematologic response and duration of hematologic response will be reported for responders.

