6 HEMATOLOGIC RESPONSE CRITERIA

Hematologic improvement is based on modified MDS IWG criteria, which is listed below.²⁴
 Improvement in counts should be sustained for at least two months and demonstrated by at least 2 consecutive measurements to be considered a hematologic response

Hematologic improvement	Response Criteria (responses must be sustained over a minimum of 8 weeks in duration)		
Erythroid response (pretreatment, <10g/dL)	Hgb increase by $\geq 1.5\text{g/dL}$ for non-transfusion dependent patients	For patients who are transfusion dependent: Transfusion independence Only transfusions given for Hgb $\leq 8\text{g/dL}$ or for symptoms will be counted in the response evaluation	
Platelet response (pretreatment, <100k/uL)	If initially $<20\text{k/uL}$ to start, then must increase to	If initially $\geq 20\text{k/uL}$ to start, then must have an absolute	

	>20k/UL with an absolute increase of 100%	increase of >30k/UL
Neutrophil response (pretreatment <1000/uL)	If initially <500/uL to start, then must increase to >500/uL with an absolute increase of >250/uL	If initially ≥500/uL to start, then must have an absolute increase of >500/uL
Progression or relapse after HI*	At least one of the following: Decrease in ANC by >50% from baseline and absolute value <1000, platelet count decrease by >50% from baseline and absolute value <100k, reduction in Hgb by ≥1.5g/dL and absolute value <10g/dL, or doubling in transfusion requirement	

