9.6 Analysis of Secondary Efficacy Endpoints

Changes in marrow cellularity pre and post treatment will be determined by a hematopathologist categorically (improvement in marrow cellularity or no improvement) and will be reported as a point estimate with 90% binomial confidence intervals.

Changes in methylcellulose colony forming assays pre and post treatment will be assessed. Mean changes will be estimated with Student's paired t-test for null hypothesis with binomial confidence intervals.

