9.8 Analysis of Exploratory Endpoints

Change in exploratory endpoints before and after treatment will be compared using a paired t-test for aldehyde-mediated damage, chromosomal breakage, and radial formation in response to DEB/MMC exposure, micronuclei formation in buccal swab samples, percentage of cells in quiescence for cell cycling in CD34+ hematopoietic stem/progenitor cells, serum insulin, fasting glucose, and oral glucose tolerance test.

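### Do the four blood-count secondary endpoints, declared as change from baseline, need a written change analysis and a stated denominator for the lineage response rates?

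*Combined protocol and SAP*

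**What the plan says.** Section 1.3 sets a secondary objective: "To evaluate the hemoglobin, RBC transfusion requirements, platelet count, and absolute neutrophil count". Section 9.1.2 then states that "Secondary hematologic endpoints will evaluate change from baseline in" six measures: those four, marrow cellularity and methylcellulose colony assays.

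The analysis sections treat them as follows.

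- Section 9.4 summarises baseline values of the four blood measures, transfusion requirements included.
- Section 9.5 gives the overall response rate in evaluable patients with a 90% binomial interval. It continues: "Estimated response rates for each individual hematologic lineage will also be reported", naming hemoglobin or red cell transfusions, platelets and neutrophils, again with 90% intervals. Time to response and duration of response follow for responders.
- Section 9.6 covers the other two: "Changes in marrow cellularity pre and post treatment will be determined by a hematopathologist categorically", and "Changes in methylcellulose colony forming assays pre and post treatment will be assessed".
- Section 9.8 covers the exploratory measures: "Change in exploratory endpoints before and after treatment will be compared using a paired t-test".

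Section 6 defines response by lineage, and each row carries a pretreatment limit, for example "Platelet response (pretreatment, <100k/uL". Section 3.1.4 admits patients with a single cytopenia. Section 4.2 defines evaluability by drug exposure, or by stopping for a drug-related reason, and not by lineage.

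**The concern.** Four of six declared endpoints seem to have no analysis in their declared form, while the exploratory assays have a named paired test. A threshold response differs from a numerical change: it misses rises below the cut-off and rises in patients who started above a row's limit. With blood counts at seven post-baseline visits and transfusions allowed as needed, the visit, the patient set and the handling of transfused patients could all be picked after the data are seen. The lineage rates add a second doubt, because a patient low only in platelets cannot be an erythroid responder but might still be counted in the erythroid denominator. At stake would be selective reporting of secondary results in a pilot that, according to Section 2.5, may lead to a larger controlled trial.

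**Working it through.** **1. The plan's own figure.** Inputs from Section 9.2: 22 evaluable patients, at least 3 responders, true rates 20% and 5%. P(X ≥ 3) = 1 − Σ C(22,x) pˣ(1−p)²²⁻ˣ over x = 0, 1, 2.

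- p = 0.20: 1 − (0.0074 + 0.0406 + 0.1065) = 0.8455; the plan states at least 0.84.
- p = 0.05: 1 − (0.3235 + 0.3746 + 0.2070) = 0.0948 (before rounding of the terms); the plan states below 10%.

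Both reproduce. They concern overall response, which does not depend on how lineage rates or count changes are reported.

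**2. Endpoint against analysis.**

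| Endpoint in 9.1.2 | Baseline summary | Post-treatment analysis |
|---|---|---|
| Hemoglobin, red cell transfusions | 9.4 | Erythroid response rate, 9.5 |
| Platelets | 9.4 | Platelet response rate, 9.5 |
| Neutrophils | 9.4 | Neutrophil response rate, 9.5 |
| Marrow cellularity | not listed | Improved or not, 9.6 |
| Colony assays | not listed | Mean change, paired t-test, 9.6 |

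Only the colony assays get a numerical change. Marrow cellularity is reduced to yes or no. The Section 6 responses are also yes-or-no changes from pretreatment: a hemoglobin rise of at least 1.5 g/dL, a platelet rise above 30k/uL (starting at 20k or more), a neutrophil rise above 500/uL (starting at 500 or more), or transfusion independence. If the marrow analysis is accepted as a form of change, so are these. What is missing is a numerical summary.

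**3. What a threshold can hide.** Sustained rises of 1.4 g/dL, 30k/uL and 500/uL in every non-transfused patient starting in those ranges would give no responders, since 1.4 < 1.5 and the other two limits are strict. These values were chosen to fall at or just under each cut-off. They show that the two measures differ, not that a loss of this kind is likely.

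**4. Denominator of a lineage rate.** The documents do not give k, the number of evaluable patients low in a lineage, so k and the three responders are assumptions. Exact (Clopper-Pearson) 90% intervals:

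| Responders / k | Rate | 90% interval |
|---|---|---|
| 3/22 | 13.6% | 3.8 to 31.6% |
| 3/15 | 20.0% | 5.7 to 44.0% |
| 3/12 | 25.0% | 7.2 to 52.7% |
| 3/8 | 37.5% | 11.1 to 71.1% |

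The numerator is the same in every row, because Section 6 does not let a patient above the limit respond in that lineage. Given the count and k, a reader can move between rows.

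**5. What a mean change would offer.** The 90% half-width in SD units is t(0.95, n−1)/√n: 1.721/√22 = 0.37 at n = 22, 1.761/√15 = 0.45 at n = 15 and 1.895/√8 = 0.67 at n = 8. The documents give no SD, so this cannot be turned into g/dL or cells/uL. It describes the precision of an added summary, not an error in the plan.

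**6. Time point.** Seven post-baseline counts are scheduled, on Days 29, 57, 85, 113, 141, 169 and 197. Day 197 is follow-up after treatment and Day 169 is the end-of-treatment visit. Sections 9.6 and 9.8 both contrast values before and after treatment, so the end-of-treatment value is the natural comparison and the other visits are available for display.

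**The case for a change.** The strongest case for a change is that lineage response is not the endpoint declared in Section 9.1.2, that the summary measure, visit and transfusion handling are unwritten, and that a few sentences would settle them without new blood tests. The observation about the text stands: no section gives a numerical change for the four measures, and the lineage sentence does not deal with patients who were not low in that lineage. Red cell transfusions are the least specified, with no comparison period named, although Section 6 supplies an eight-week duration and a rule on which transfusions count.

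The inferences drawn from this are weaker. The secondary objective asks only for evaluation of these measures, and lineage rates with intervals, plus time to response and duration, go some way to meet it. The evaluable population named in the preceding sentence of Section 9.5 carries over naturally, and Section 6 leads any analyst to show how many patients were low in each lineage.

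The obvious written rule also has a cost. Limiting the change to patients with a Day 169 value could leave out those removed early under Section 5.5, which lists sustained worsening of cytopenias as a reason for removal. The mean would then lean in a favourable direction, and reporting the number missing would not correct it.

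**Conclusion.** No change to the plan follows. This is missing detail that analysts can fill sensibly: the declared endpoint already asks for change from baseline, the counts are scheduled, the baseline values are already to be tabulated, and Section 6 identifies who can respond in each lineage. No written rule gives a wrong result.

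The effect is confined to descriptive secondary results. On assumed inputs, three lineage responders could read as 13.6% or 37.5% depending on whether 22 or 8 patients are counted, which a stated denominator makes plain. The overall response rate, its 90% interval, the 3-in-22 rule and the sample size do not move.

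This conclusion assumes that the report shows lineage denominators, summarises the scheduled counts rather than one favourable visit, and treats the results as descriptive. That fits Section 2.5, which says this small single-arm study cannot settle clinical benefit. It would not extend to a confirmatory claim based on these four endpoints, and the plan makes none.
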